#### 1. Introduction and Purpose:

Anemia in pregnancy affects 18-21% of pregnant women in the United States and is associated with low birth weight, preterm delivery, and perinatal mortality as well as a possible association with postpartum depression and poor mental and psychomotor performance testing of offspring. Current treatment of iron deficiency anemia in pregnancy consists of daily iron supplementation with the intent of raising hemoglobin back to normal ranges. A recent review examining misconceptions in the management of iron deficiency described the misconception of high dose daily iron supplementation noting, "low daily doses (e.g. 50 mg) or moderate doses (e.g. 100 mg) every other day may increase both tolerance and efficacy of oral iron supplementation" (1). Further commentaries call for continuing research into every other day dosing (2). Given the prevalence and complications of iron deficiency anemia in pregnancy, we propose to study if alternate day dosing of oral iron supplementation is statistically superior or at least not inferior to daily dosing in raising third trimester hemoglobin.

#### Brief Study Design and Rationale

Two randomly assigned groups will be compared during the antepartum period:

- 1. Control Group: standard of care, daily oral iron supplementation of ferrous sulfate 325 mg (65 mg elemental iron) taken by mouth once daily.
- 2. Intervention Group: alternate day dosing oral iron supplementation of ferrous sulfate 650 mg (130 mg elemental iron) taken by mouth every other day.

Historically twice or thrice daily oral iron supplementation has been the recommended as the first line treatment of iron deficiency anemia. This standard of care for oral iron therapy is starting to change (1, 2) with some current textbooks and guidelines recommending either daily or every other day dosing regimens (3, 4). The standard of care at UTMB for the detection and treatment of iron deficiency anemia is as follows. All pregnant patients undergo blood draws at their first appointment for anemia screening. Those patients who are identified as anemic then undergo further studies to determine the type of anemia. Those patients determined to have iron deficiency anemia receive oral iron supplementation. There are many different iron supplements that are used at UTMB to treat iron deficiency in pregnancy. These supplements vary in elemental iron content, enteral coatings, and supplements combined with vitamins and minerals. The choice of which iron supplement that patients receive is left to the discretion of the provider caring for the patient. Among these choices, ferrous sulfate (325mg, with 65mg elemental iron) is very commonly prescribed to UTMB patients and thus is the oral iron therapy that will be used for this study. Standard UTMB treatment surveillance includes blood draws at least every trimester or more frequently based on symptomatology of patient and provider discretion. This study will follow the UTMB standard treatment surveillance protocol and thus study participants will have no study specific blood collections. As part of this standard surveillance if hemoglobin levels remain low patients may be considered for more aggressive treatments such as IV iron infusion or transfusion. The decision to escalate treatment takes into account risk of cesarean delivery and risk of obstetric hemorrhage among other considerations and will be left to the discretion of the provider.

#### Primary outcomes:

• Change in hemoglobin and hematocrit in the 3rd trimester

### Secondary outcomes:

- Assessment of GI adverse effects determined by survey
- Analysis of CBC indices including reticulocyte count, MCV, etc.
- Iron studies at time of diagnosis
- Need for parental iron supplementation
- Need for transfusion in the peripartum period
- Postpartum hemoglobin and hematocrit
- Neonatal weight
- Presence of antepartum fetal growth restriction
- Neonatal outcomes such as NICU admission, hyperbilirubinemia, and APGAR scores
- Relationship of obesity to effectiveness of supplementation in both study arms

### Study Risks and Benefits:

The known risks of oral iron therapy are gastrointestinal upset such as nausea and vomiting, constipation, and abdominal pain. Oral iron supplementation for the treatment of iron deficiency anemia in pregnancy is the standard of care and as such has been demonstrated to be a safe and effective treatment. Studies have demonstrated that intermittent dosing of oral iron can result in increased iron absorption, however this has not been studied in a pregnant population (5, 6).

### 2. Background:

The prevalence of iron deficiency anemia (IDA) in reproductive aged women aged 20-49 years is estimated to be 9.2% (7). In pregnancy, rates of anemia affect between 18-21% of pregnant women in the United States with non-Hispanic blacks and teenage mothers affected at even higher rates (8, 9). Outside of pregnancy anemia has been estimated to account for 8.8% of global disability (10). However, during pregnancy IDA has been associated with increased risk of low birth weight, preterm delivery, and perinatal mortality as well as a possible association with postpartum depression and poor mental and psychomotor performance testing of offspring (8). Gabbe et al. notes that "In developing nations, severe anemia is alarmingly common and is a major cause of maternal morbidity and mortality" (11). Pregnant patients with anemia are at further risk for blood transfusion in the event of postpartum hemorrhage.

In pregnancy, hematology physiology changes drastically. Total blood volume increases by approximately 50% and red blood cell mass increases by 25% (8). The relative increase of blood volume compared to red blood cell mass causes a physiologic anemia of pregnancy and therefore the hemoglobin and hematocrit threshold for diagnosing anemia in pregnancy are different than that of a non-pregnant adult (8). This increase in red blood cell mass, combined with the needs of the fetus, placenta, and normal anticipated blood loss from vaginal delivery represent a total additional need of 1,000 mg iron for a pregnancy. It is therefore, unsurprising that the most common etiology of anemia in pregnancy is iron deficiency, representing 75% of all anemia in pregnancy (11).

The World Health Organization (WHO) recommends that pregnant women take 60 mg elemental iron daily while noting that 30 mg might be sufficient (12, 13). The American College of Obstetrics and Gynecology (ACOG) however notes that, "It is unclear whether iron supplementation in well-nourished pregnant women who are not anemic affects perinatal outcomes" (8). Most pregnant women receive some level of iron supplementation through the administration of prenatal vitamins.

The definitive diagnosis of iron deficiency should be made with measurement of serum iron, ferritin, and transferrin saturation; however, recent iron therapy and extended periods of anemia can complicate the interpretation of these results (11). The diagnosis of iron deficiency is often presumed in pregnant patients with

a hemoglobin below 11 g/dl in the first trimester and/or 10.5 g/dl in the second trimester and iron therapy is often empirically started without first obtaining iron studies (8).

For iron deficient anemic individuals, the current recommendation for treatment by the CDC is oral supplementation of 60-120 mg of elemental iron daily (14). However this regimen is being questioned with some sources recommending every other day dosing (3, 4, 15). Ideally response to supplementation should be seen in about 3 weeks in a non-pregnant patient (16). In pregnancy response of an anemic patient to oral iron therapy should be seen with reticulocytosis after 3-10 days and hemoglobin should begin to increase within one week (11, 17). Iron stores however may take 1 month or longer to replenish (11, 18). Of note, obese patients have been found to have decreased iron stores thought to be secondary to an inflammatory response from obesity and increased levels of Hepcidin (19).

While generally considered safe, oral iron supplementation can be commonly associated with adverse gastrointestinal complaints including metallic taste, nausea, vomiting, heartburn, epigastric pain, diarrhea, and constipation (20).

Early studies have begun to question the effectiveness of daily iron supplementation in IDA. Internationally, studies conducted in Malawi (2000) and China (1996) for anemic and non-anemic pregnancy women demonstrated no difference between outcomes (21, 22). A 2015 Cochrane review examined intermittent iron supplementation in anemic concluded that there was no benefit to intermittent supplementation, however this review was limited by a small number of poor quality studies included in the meta-analysis (23). Faced with the obvious limitations of these studies, a more systematic investigation into the physiology and biochemistry of oral iron supplementation was then described. The absorption of iron is a tightly regulated process with hepcidin, the principal iron regulatory hormone, functioning to inhibit iron absorption in the gut (20, 24). In pregnancy, hepcidin levels have been demonstrated to be lower (25). In response to elevated iron stores, hepcidin levels increase thereby inhibiting further systemic iron absorption (26). Recent data has described that oral iron supplementation can increase hepcidin levels as well. In 2015, a study demonstrated that after oral iron supplementation of 60 mg elemental iron or greater, hepcidin levels increased for the next 24 hours which in turn decreased the fractional iron absorption (27). A follow-up study in non-anemic, iron deficient women demonstrated that the inhibitory effect of hepcidin on daily iron dosing could be overcome with single day dosing on alternate days with increased cumulative iron absorption in the alternate day dosing group (6). This study was further strengthened with a similar trial, this time in iron-deficient, anemic women which demonstrated that alternate day of 100-200 mg elemental iron resulted in higher fractional iron absorption with lower GI side effects when comparted to daily dosing (5). Based on studies such as these, some experts have suggested the current treatment of iron therapy may be incorrect, and that alternate day dosing might be beneficial, though further studies are needed (1, 2, 4, 16, 20, 28). Several similar studies are currently in process at this time, links listed in the references section (29-32).

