## 3. Concise Summary of Project:

This trial will be a comparative pragmatic open label randomized controlled trial of daily versus alternate day dosing of oral iron in anemic pregnant patients.

Two randomly assigned groups will be compared during the antepartum period:

- 1. Control Group: standard of care, daily oral iron supplementation (325 mg PO daily ferrous sulfate)
- 2. Intervention Group: alternate day dosing oral iron supplementation (650 mg PO every other day ferrous sulfate)

325mg Ferrous sulfate is a standard oral iron supplement providing 65 mg of elemental iron per dose. Standard dosing recommendations for the treatment of iron deficiency anemia is between 65 to 200 mg elemental iron daily.

Each group will receive a phone survey 2-4 weeks after initiation of therapy to assess side effects of each group as well as compliance. Call is anticipated to last approximately 10-15 minutes. This survey has previously been validated in assessing gastrointestinal symptoms for those taking oral iron supplementation (33).

The number of subjects studied will be 86 subjects at UTMB, we plan to approach and consent up to 96 patients to allow for screening failures, early withdrawals, and patients lost to follow-up, and patients who must withdraw due to failure of therapy. Failure of therapy for the purposes of this study will be patients who require parental iron supplementation or transfusion. Study to last an anticipated length of 3 years. If our sample size is not achieved, we will submit to the IRB an addendum to increase the number of consented subjects to achieve the desired sample size.

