#### Screening

All pregnant patients undergo a laboratory screen for anemia at the first prenatal appointment as part of the UTMB standard of care. Eligible patients (1st or 2nd trimester patients with a hemoglobin below 11 g/dl or 10.5 g/dl respectively) will be screened and approached at their next prenatal appointment for consent (detailed under section 9). We request a waiver to screen these patients.

The anticipated procedures flow is as follows

- 1. Research staff will travel to location
- 2. Research staff will confirm with provider that possible subjects are appropriate candidates for treatment with ferrous sulfate
- 3. Research staff will approach screened patients to obtain consent from possible subjects
- 4. Subjects will be randomized using a randomization log with group assignment, subject name, and medical record number
  - a. Daily dosing group will take ferrous sulfate 325 mg (65 mg elemental iron) by mouth daily
  - b. Alternate day dosing group will take ferrous sulfate 650 mg (130 mg elemental iron) by mouth every other day
- 5. Prescriptions for the appropriate regimen will be provided by the research staff
  - a. If the research staff is a physician, the appropriate prescription will be sent at time of encounter
  - b. If the research staff is a non-physician, a physician research staff member will be alerted and the appropriate prescription will be sent on the same day
- 6. After patient is consented and enrolled, the provider will be notified and a note will be placed in the electronic chart indicating that the patient is enrolled in the study.

- 7. Subjects will continue to receive standard, routine prenatal care and surveillance of iron deficiency anemia in pregnancy
  - a. Research staff and PI will monitor surveillance data by chart review
- 8. 2-4 weeks after initiation of respective iron regimen research staff will contact subjects by phone to administer a 5-10 min survey to assess GI side effects and compliance with regimen.
- 9. Research staff will conduct chart review to obtain the datapoints for the primary and secondary outcomes (described in section 1)

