#### Additional details

The routine prenatal visits for pregnant patients with anemia include at least monthly venipunctures to monitor the treatment of anemia and intervene if necessary. Our primary outcome of 3rd trimester hemoglobin as well as laboratory secondary outcomes are convenient data points collected in the standard treatment and surveillance of anemia in pregnancy. As such patients will not need any study specific venipuncture or visits. Prenatal visits are frequent with monthly visits in the 1st trimester, bi-monthly visits in the 2nd trimester, and weekly visits in the 3rd trimester with 24 hour after hours care phone services available. The frequency and ready availability of appointments ensures that any symptomatic patient will quickly be seen and evaluated.

Any subject that requires escalation of treatment beyond oral supplementation (IV iron infusion or blood transfusion) will be referred to receive appropriate intervention. These subjects will still be included in the intent-to-treat analysis. The routine surveillance of anemic pregnant patients described above ensures that any treatment failure will be quickly identified and addressed.

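### The arms differ only in iron schedule, yet other oral iron and later changes of oral iron are not listed for collection, so a noninferior result could not be told apart from arms that converged

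*Combined protocol and SAP*

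**What the plan says.** The regimens are set out in Section 4 under Screening. For control: "Daily dosing group will take ferrous sulfate 325 mg (65 mg elemental iron) by mouth daily". For intervention: "Alternate day dosing group will take ferrous sulfate 650 mg (130 mg elemental iron) by mouth every other day". The rationale in Section 2 is that "after oral iron supplementation of 60 mg elemental iron or greater, hepcidin levels increased for the next 24 hours", which lowers absorption of the next dose and which dosing on alternate days is meant to overcome.

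On other iron, Section 2 says: "Most pregnant women receive some level of iron supplementation through the administration of prenatal vitamins". That is the only mention of prenatal vitamins, and no dose or frequency is given. Other oral iron does not appear in the outcomes (Section 1), the study procedures or data description (Section 4), or the eligibility criteria (Sections 6 and 7).

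On care after randomization, Screening says: "Subjects will continue to receive standard, routine prenatal care and surveillance of iron deficiency anemia in pregnancy". Describing usual care at the center, Brief Study Design and Rationale says: "The choice of which iron supplement that patients receive is left to the discretion of the provider caring for the patient". Only parenteral iron and transfusion are treated as a change of therapy. Section 3 says: "Failure of therapy for the purposes of this study will be patients who require parental iron supplementation or transfusion". Additional details (Section 4) uses the same scope, "Any subject that requires escalation of treatment beyond oral supplementation (IV iron infusion or blood transfusion", and keeps those women in the intention-to-treat analysis.

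Compliance is assessed once, by phone at 2-4 weeks. Section 14 states an intention-to-treat primary analysis with noninferiority first, against a limit of -1. It names no analysis by regimen followed and makes no use of the compliance answers.

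**The concern.** When two arms carry the same iron and differ only in timing, iron from any other source, or a change of the oral regimen, acts directly on the contrast under test. Enrollment is in the first or second trimester and the outcome is third-trimester hemoglobin, so a departure after the early call can persist for much of the treatment period without being a listed data item.

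The direction matters. If some women assigned to alternate days in effect take iron daily, the arms become more alike. In a superiority test that costs power. In a noninferiority test under intention-to-treat it makes success easier. The trial is open label and hemoglobin is monitored during care. Any oral change made because of a poor response would therefore fall on the women in whom the assigned schedule was doing worst. A noninferior result could then be credited to alternate-day dosing with no data to show whether it was followed.

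**Working it through.** **1. The contrast.** Control: 65 mg x 2 = 130 mg per two days. Intervention: 130 mg x 1 = 130 mg per two days. Total iron is equal; only the schedule differs.

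**2. What background iron could do.** The documents give no vitamin iron content. As an assumed range only, take the 30 and 60 mg daily figures that Section 2 attributes to WHO (a supplementation recommendation, not vitamin content).

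| Assumed background iron | Control, each day | Alternate-day arm, on day | Alternate-day arm, off day |
|---|---|---|---|
| 30 mg daily | 65 + 30 = 95 mg | 130 + 30 = 160 mg | 30 mg |
| 60 mg daily | 65 + 60 = 125 mg | 130 + 60 = 190 mg | 60 mg |

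Only at 60 mg does the off-day amount reach the level at which Section 2 reports a hepcidin effect.

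**3. The plan's own sample sizes.** Section 14 gives 68 in total for noninferiority and 39 per group for superiority, beside a historical value of 10.27 ± 1 g/dL. Reading ± 1 as the SD:
- Noninferiority: n per arm = 2 x (1.645 + 1.282)² x 1² / 1² = 17.1, so 18 (36 in total).
- Superiority: n per arm = 2 x (1.960 + 1.282)² x 1² / 1² = 21.0, so 22 (44 in total).

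Neither stated figure is reproduced. They imply an SD of √(34/2) / 2.926 = 1.41 and √(39/2) / 3.242 = 1.36. This is a separate matter, but it is why both SD 1 and SD 1.36 are used below.

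**4. Illustration of dilution.** Assume that alternate-day dosing, if followed, is worse by exactly the margin (D = 1 g/dL), that a share f of that arm crosses to daily iron, and that each such woman recovers the full difference. The expected deficit is D(1 - f), and

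P(declare noninferiority) = Φ[(1 - D(1 - f)) / (SD x √(2/39)) - 1.645].

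The standard error is 0.226 at SD 1 and 0.308 at SD 1.36. For f = 0.2 at SD 1: (1 - 0.8)/0.226 - 1.645 = -0.76, so 22.3%. The last column is power for a true advantage of 1 g/dL diluted to 1 - f, that is Φ[(1 - f)/0.308 - 1.960].

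| f (assumed) | False noninferiority, SD 1 | False noninferiority, SD 1.36 | Superiority power, SD 1.36 |
|---|---|---|---|
| 0 | 5.0% | 5.0% | 90.1% |
| 10% | 11.4% | 9.3% | 83.2% |
| 20% | 22.3% | 16.0% | 73.8% |
| 30% | 37.4% | 25.1% | 62.3% |

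If women who cross recover only half the difference, f = 20% acts like f = 10%: 11.4% at SD 1.

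**The case against.** The case on the other side is substantial, and much of it stands.

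- **Pragmatic comparison.** The trial is declared pragmatic, and randomization balances vitamin use on average. Background vitamins therefore need not bias a comparison of two schedules added to usual care. This stands. What remains is a limit on attribution to the schedule itself.
- **Unknown vitamin dose.** A reader might infer that prenatal vitamins turn the alternate-day arm into a daily-iron arm. The documents do not support that. Section 2 speaks of some iron in most pregnant women generally, gives no amount or frequency, and reports the hepcidin effect only from 60 mg.
- **Provider changes.** A reader might infer that providers will switch women to daily oral iron. This too is inference, from usual-care discretion and the absence of any rule. The escalation described is IV iron or transfusion. Research physicians write the prescriptions, providers are educated about the trial and notified of enrollment, and a chart note is placed.
- **Early survey.** It would go too far to say that nothing is recorded. The call assesses compliance and may catch early departures. Its compliance questions are not in the documents, and it cannot see later changes.
- **The illustration.** The crossover rates have no source. The model gives each woman who crosses the full benefit of daily iron, although a switch after a low hemoglobin gives only partial exposure. It also allows no added oral iron in the control arm, which would widen the difference.

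None of this supplies the missing data. Randomization does not balance changes made afterward in response to hemoglobin.

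**Conclusion.** The point holds as a gap in measurement and supportive analysis, not as a demonstrated bias. Non-study oral iron and changes of oral iron through the third trimester are not listed for collection, no analysis uses the regimen actually followed, and noninferiority is tested first on intention-to-treat alone. Loss of contrast would favor noninferiority, count against superiority and go undetected.

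The size is conditional: roughly 11-37% false noninferiority in place of 5% at SD 1, or 9-25% at SD 1.36, for 10-30% crossover with full recovery at a true deficit equal to the margin. These figures show sensitivity and do not predict the trial's error rate. They concern crossover, not vitamin use. The change is worth making because it is cheap and widens what a noninferior result can support.

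**What to change.** 1. **Record.** At consent and in the existing phone survey, record product, elemental iron content and frequency of prenatal-vitamin and other oral iron. In the chart review, record every dated change of oral iron product, dose or frequency through the third-trimester hemoglobin.
2. **Report.** Show these data by arm as descriptive results, separate from the failure-of-therapy definition.
3. **Analyze.** Keep intention-to-treat as primary. Prespecify a supportive noninferiority analysis by regimen actually followed, and claim noninferiority with confidence only if the two agree. Excluding poor responders who switched can itself push the result toward noninferiority, so add a sensitivity analysis that uses their last hemoglobin before the change.
4. **Word the conclusion** as a ferrous sulfate schedule added to background prenatal iron.

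Section 3 speaks of patients who must withdraw because therapy failed, while Additional details keeps escalated women in the intention-to-treat analysis. These passages should be reconciled. No change to prescribing or to the clinical failure rule is proposed.

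The cost is a few data fields in contacts and reviews already planned, one small supportive analysis and a slightly narrower conclusion.
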